8.13 Study schedule (table)

	Baseline	3 Months**	6 Months**
Clinical /Virtual Clinic Follow-up	X	X	X
CBC with Diff Basic Metabolic Panel (BMP) LFTs	X	X	X
ECG	X	X	X

Pregnancy Test ^ (for females of childbearing age)	X	X	X
Echocardiography (CHD group)	X	X	X
Echocardiography (CS group)	X		X
Plasma collection for 5-HIAA	X	X	X
NT-proBNP	X	X	X
Hs-troponin T	X	X	X
6 minute walk test	X	X	X
MDASI	X	X	X
Depression Assessment	X	X	X

(**-asterisk- labs and tests maybe done 3 weeks prior or up to 3 weeks after clinical baseline/follow-up date. ^- pregnancy test will be within one week of visit)

8.14 Call schedule during study

Patients will be called by Research team once a week for the first month after baseline and monthly afterwards except for the months with clinical visit (3 month visit, 6 month visit) to assess for potential toxicities, adverse events, treatment compliance, and answer patient questions.

*Research Phone Calls have a time window of +/- 1 business day to account for institutional holidays and subject availability.

*Patients with adverse events noted on the call will be called every week until the adverse events resolve.

*If a dosage change is made after the first month the patient will be called the following week for assessment.

	Research Call	Clinical Visit
Week 0 (Baseline)		X
Week 1	X	

Week 2	X	
Week 3	X	
Week 4	X	
Week 8	X	
Week 12 (3 months)		X
Week 16	X	
Week 20	X	
Week 24 (6 months)		X

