6.3.2 Dose Adjustments for adverse events related to the study drug

Adverse Events will be graded as follows (NCI CTCAE version 5.0)

Grade 1 No change in dose
Grade 2 Hold until ≤Grade 1. Resume at same dose level.
Grade 3 Hold until ≤Grade 1. Resume at 1 dose level lower (250 mg tid).
Grade 4 Hold and contact the Primary Investigator

Dose can also be adjusted or discontinued per PI's discretion for patients' safety.

*Patients unable to tolerate 250 mg tid should be discontinued from telotristat ethyl. **Constipation and abdominal pain dose adjustment is different (see below)

6.3.3 Recommended management for the following AEs:**6.3.3.1** Nausea and/or vomiting: treatment with antiemetics**6.3.3.2** Diarrhea: treat underlying cause and/or with antidiarrheal**6.3.3.3** Gastrointestinal toxicity**6.3.3.3.1** Monitor concomitant medication usage**6.3.3.3.2** Constipation (Grade 1 and above): initiate treatment as clinically indicated; examples of therapies include: laxatives, enemas, suppositories, psyllium hydration, over-the-counter (OTC) agents**6.3.3.3.3** Abdominal pain (Grade 1 and above): initiate treatment as clinically indicated; examples of therapies) include: analgesics, anti-gas/bloating agents**6.3.3.3.4** Hold telotristat ethyl for Grade 2 constipation or abdominal pain until \leq Grade 1.**6.3.3.3.5** Discontinue telotristat ethyl for Grade 3 constipation or abdominal pain*(please note this is different than above table)**6.3.3.4** Suicidal ideation: discontinue telotristat ethyl**6.4 Treatment Compliance**

Patients will be asked to bring their unused or unopened bottles of telotristat ethyl to each visit. Patients will be allowed to ship their unused and/or unopened bottles of telotristat ethyl back to PI at MDAnderson if traveling is impossible/restricted. At each visit study site personnel will count returned tablets and reconcile the counts against planned number of doses for that interval. All dosages prescribed and dispensed to the patient, dose modification(s), and missed dose(s), including planned dose interruptions during the study must be recorded. Site personnel are to clarify any discrepancy and record this information.

Patients must maintain at least 70% compliance at clinical visits (3 month interval including allowed window; see section 8 for details) in dosing to be deemed as compliant.

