6.6 Duration of Therapy

The total duration of therapy with the study drug telotristat ethyl will be 6 months as part of the clinical trial assessment.

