8.0 Evaluation during Study

- 8.1 Complete history and physical examination done at 3 and 6 months as part of clinical follow-up. (telemedicine technology and language assistant may be used)
**A window of 3 weeks before or after for these visits will be acceptable to accommodate for patient convenience.
- 8.2 CBC with differential, Liver panel (to include AST, ALT, bilirubin, albumin), basic metabolic panel (Sodium, potassium, bicarbonate, chloride, BUN, creatinine, glucose) done at 3 and 6 month (**-asterisk- labs and tests maybe done 3 weeks prior or up to 3 weeks after clinical follow-up date)
- 8.3 ECG done at 3 and 6 months within 6 weeks of clinical visit**
- 8.4 Pregnancy test for females of childbearing age within one week
- 8.5 MDASI done at 3 and 6 months (telemedicine technology and language assistant may be used;can be done within 6 weeks of clinical follow-up)
- 8.6 Echocardiography with a 2D transthoracic echocardiography (2D TTE), 3-dimensional echocardiography (3D TTE), and myocardial strain of the left and right ventricle to be done at 3 and 6 months for those patients with carcinoid heart disease and with carcinoid syndrome and high suspicion of carcinoid heart disease (CHD group), such as those with clinical features or increased NT-proBNP (> 260) mg/ml and/or 5-HIAA levels (24 hr urine 5-HIAA > 100 mg). (**- asterisk- labs and tests maybe done 3 weeks prior or up to 3 weeks after clinical follow-up date
- 8.7 Echocardiography will be done at 6 months in patients with carcinoid syndrome (CS group) who do not have high suspicion for carcinoid heart disease

8.8 Plasma 5-HIAA collection at 3 and 6 months (**-asterisk- labs and tests maybe done 3 weeks prior or up to 3 weeks after clinical follow-up date) (it will be kept frozen in Cryogene lab and will be transferred to Frontage Lab for analysis. More information is included in the lab manual.)

8.9 Cardiac biomarkers to include: N-terminal pro B-type natriuretic peptide (NT-proBNP) and high sensitivity troponin T (HS-troponin T) at 3 and 6 months (**-asterisk- labs and tests maybe done 3 weeks prior or up to 3 weeks after clinical baseline/follow-up date)

8.10 6 minute walk test (6MWT) where distance is recorded in meters at 3 and 6 months (**-asterisk- labs and tests maybe done 3 weeks prior or up to 3 weeks after clinical follow-up date)

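### An early 3-month visit (Week 9) replaces the Week 12 call, so the next listed safety contact can be 50 to 52 days later, against 29 to 31 when the visit is on time

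*Combined protocol and SAP*

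**What the plan says.** Section 8.14 sets the contact schedule between visits. Calls are weekly in the first month and then "monthly afterwards except for the months with clinical visit (3 month visit, 6 month visit"). The table lists calls at Weeks 1, 2, 3, 4, 8, 16 and 20 and clinical visits at Weeks 0, 12 and 24. The purpose given for the calls is to check for toxicities, adverse events and compliance and to answer questions.

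The two kinds of contact have very different windows. For calls: "Research Phone Calls have a time window of +/- 1 business day to account for institutional holidays and subject availability". For the 3- and 6-month visits, section 8.1 says: "A window of 3 weeks before or after for these visits will be acceptable to accommodate for patient convenience".

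Section 8.14 has two rules for extra calls: "Patients with adverse events noted on the call will be called every week until the adverse events resolve", and "If a dosage change is made after the first month the patient will be called the following week for assessment".

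On treatment, section 6.6 states: "The total duration of therapy with the study drug telotristat ethyl will be 6 months as part of the clinical trial assessment". Section 6.3.3 includes two instructions that depend on the team knowing of an event: "Hold telotristat ethyl for Grade 2 constipation or abdominal pain until" Grade 1 or lower is reached, and "Discontinue telotristat ethyl for Grade 3 constipation or abdominal pain".

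**The concern.** The Week 12 call is left out because a visit is expected at about that time, but the visit is not tied to Week 12. If it is held at Week 9, it still falls in the third four-week month, so no other contact is listed for that month. Nothing in 8.14 adds a Week 12 call or brings the Week 16 call forward.

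The extra-call rules do not fill the gap for a patient who has had no adverse event noted on a call and no dose change. Such a patient can go about 7 weeks on blinded treatment without a scheduled safety question, although 8.14 otherwise sets up roughly monthly contact.

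What is at stake is delay in learning of an event. Holding the drug for Grade 2, or stopping it for Grade 3, constipation or abdominal pain can happen only once the team has been told. For a patient who does not call in, an event that starts soon after an early visit may first be asked about some 3 weeks later than the nominal schedule intends.

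**Working it through.** **Inputs.** The Week 12 visit is day 84 and the Week 16 call is day 112 (8.14 table, counted from Week 0). The visit window is 21 days either way (8.1), so the earliest 3-month visit is day 84 − 21 = day 63, or Week 9. The call window is 1 business day (8.14). That is 1 calendar day in midweek and 3 across a weekend. Baseline is taken to be on a weekday, with no holiday on the relevant dates.

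**The plan's own spacing.** Visit on time: 112 − 84 = 28 days. With the Week 16 call 1 business day late, this is 28 + 1 = 29 days for a Monday to Thursday baseline. For a Friday baseline the call moves to Monday, giving 28 + 3 = 31 days. The like-for-like range is therefore 29 to 31 days.

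**Early visit.** The formula is gap = 112 + (1 to 3) − visit day.

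| 3-month visit | Day | Nominal gap to Week 16 call | With a late call |
|---|---|---|---|
| Week 12 (on time) | 84 | 28 | 29 to 31 |
| Week 11 | 77 | 35 | 36 to 38 |
| Week 10 | 70 | 42 | 43 to 45 |
| Week 9 | 63 | 49 | 50 to 52 |

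The largest lengthening is 49 − 28 = 21 days.

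**Is this time on drug?** 8.14 equates 6 months with Week 24, and 6.6 sets treatment at 6 months. Weeks 9 to 16 therefore lie wholly within the treatment period.

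**Ordinary call-to-call maximum.** Two calls 4 weeks apart, the first 1 business day early and the second 1 business day late, are 28 + 1 + 1 = 30 days apart for a Tuesday to Thursday baseline. They are 28 + 3 + 1 = 32 days apart for a Monday or Friday baseline. This 30 to 32 is the longest gap between listed contacts when visits are on time (Week 4 to 8, or Week 16 to 20). It is not the visit-to-Week-16 interval.

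**With a Week 12 call kept.** Week 9 visit to Week 12 call: 84 − 63 = 21 days, or 22 to 24 with a late call. Week 12 call to Week 16 call: 30 to 32 days at the edges of both windows. The longest gap after an early visit is then 30 to 32 days.

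**The case against.** The strongest reply is that nothing has gone wrong. The visit window is a deliberate concession to patients, the protocol states no maximum interval between contacts, and an early visit moves a contact without removing one. By Week 9 the patient has had calls at Weeks 1, 2, 3, 4 and 8 and then a visit with history, examination and laboratory tests. Adverse events noted on a call bring weekly calls. Patients continue somatostatin analog therapy, with stated doses every 4 weeks, and laboratory tests may be done up to 3 weeks after the visit, so other contact is likely. Section 11.3 reports a similar incidence of treatment-related adverse events among all groups in phase 3. A DSMB is named in 12.0, and serious adverse events are captured until 30 days after the last dose.

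Most of this stands, and it is why the point is minor. It does not close the gap. The documents do not say who gives the injections, and neither injections nor laboratory tests are scheduled safety questions. Serious-event capture and the DSMB act on what the team has learned.

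A reader might go further and infer that late visits produce the same gap: Week 8 call to a Week 15 visit, or Week 20 call to a Week 27 visit. The documents do not settle this. If the visit slips out of its month, the sentence in 8.14 can be read as making a call due in that month, and the long gap arises only if the table is followed instead. For Week 27, the last 3 weeks may also fall after dosing has ended.

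**Conclusion.** The point holds in a limited form. Sections 8.1 and 8.14 together permit 49 days on study drug between listed safety contacts (50 to 52 with the call window) after a 3-month visit at Week 9. The same interval is 28 days (29 to 31) when the visit is on time. This assumes that weeks are counted from baseline as in the table, that neither extra-call rule is triggered, and that no holiday falls on the call date. A holiday Monday would turn 52 days into 53.

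This is an optional improvement of low severity. A reader might infer that a safety requirement is breached, but none is stated. A reader might also infer an effect on the trial's main result; the primary endpoint does not depend on the calls. Nor can the number affected be read from section 11.1. At the time of that count, 13 + 3 + 19 = 35 of 79 patients were in follow-up, awaiting randomization or still to enroll. That is only an upper bound before drop-out. Some of the 13 may already have passed the 3-month visit, and the gap arises only when that visit is early. The documents do not say how often that happens, or whether any event would be missed.

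**What to change.** Add one sentence to 8.14: if the 3-month visit is held before Week 12 by more than 1 business day, the Week 12 research call is still made. The same sentence can say that a call is due at Week 12 if the 3-month visit has not yet taken place, which settles the reading for late visits. No Week 24 rule is needed for this point.

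The cost is one extra call, by existing staff, for each patient whose 3-month visit is moved. The 3-week visit window in 8.1 is unchanged. The sentence helps only patients who have not yet passed that visit.

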9.0 Criteria for response/change

9.1 Biochemical response/change.

9.1.1 5-HIAA levels- response will be defined as a reduction in plasma 5-HIAA of 30%

9.1.2 Change in NT-ProBNP

9.1.3 Change in HS-troponin T

9.2 Echocardiographic response

9.2.1 Echocardiographic scoring system for CVHD- response will be defined as a change in CVHD score of 10%

9.2.2 Myocardial strain assessment- response will be defined as a change in global longitudinal strain by 15%

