2.0 Objectives

The purpose of the study is to evaluate the effect of telotristat ethyl (XERMELO) + somatostatin analog (SSA) (Treatment arm) versus placebo + SSA (standard of care arm) in patients with carcinoid syndrome and carcinoid heart disease. The study will be conducted in agreement with Good Clinical Practice guidelines and the Declaration of Helsinki and be submitted for approval to the MD Anderson Cancer Center IRB before initiation.

Primary Objective:

1. To estimate the percent change in NT-proBNP at 6 month visit from baseline after initiation of study drug in each arm and to compare the percent change between the two study arms.

Secondary Objectives:

1. To evaluate the change in functional capacity from baseline at 3 and 6 month visits as assessed by a 6 minute walk test (6MWT) in each arm
2. To evaluate changes in echocardiographic parameters (CVHD score, global longitudinal myocardial strain assessment of the Left and right ventricle/TAPSE) from baseline to 3 and 6 month visits in each arm
 - a. Carcinoid Valvular Heart Disease (CVHD) score is determined by 1) tricuspid valve appearance, 2) tricuspid regurgitation severity by either spectral pulsed wave or color Doppler flow mapping; 3) pulmonary stenosis severity by spectral pulsed or continuous wave Doppler, and 4) pulmonary insufficiency severity by color Doppler. (Denney et al. JACC 1998)
 - b. Global longitudinal myocardial strain assessment will be conducted using GE Vivid echocardiography machines in all studies. Significant change will be defined as a change in global longitudinal strain by 15%.
 - c. TAPSE will be defined as normal ($\geq 1.6\text{cm}$) or abnormal ($< 1.6\text{cm}$)

3. To evaluate the change from baseline to 3 and 6 month visits in Plasma 5-hydroxyindoleacetic Acid (5-HIAA) levels in each arm. 5-HIAA is a standard test used in clinical practice to assess neuroendocrine tumor (NET) activity.
4. To evaluate the change from baseline to 3 and 6 month visits in high sensitivity troponin T in each arm
5. To evaluate the change from baseline to 3 and 6 month visits in health related quality of life with using the MD Anderson Symptom Inventory (MDASI) in each arm
6. To evaluate compliance of medications

Primary endpoint: The percent change in NT-proBNP at 6 month visit from baseline

Secondary Endpoints:

1. The change in 6MWT from baseline at 3 and 6 months

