2. The change in CVHD score from baseline at 3 and 6 months , change (significant change or non-significant change) in global longitudinal myocardial strain assessment of the left and right ventricle from baseline at 3 and 6 months, change (normal or abnormal) in TAPSE from baseline at 3 and 6 months
3. The change in plasma 5-HIAA levels from baseline at 3 and 6 months
4. The change in high sensitivity troponin T from baseline at 3 and 6 months
5. The change in quality of life questionnaire (using MD Anderson Symptom Inventory (MDASI)) from baseline at 3 and 6 months
6. The proportion of patients maintaining at least 70% compliance

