11.2 Statistical Analysis Plan

We will analyze two analysis sets, including modified intention-to-treat and per protocol analysis sets. Modified intention-to-treat analysis set will include all patients who were randomized and started a study treatment, regardless of whether they received treatment as planned. Per protocol analysis set will include all patients who received treatment as planned.

Patient baseline characteristics and outcome variables (primary endpoint and secondary endpoints (absolute changes and percent changes for continuous endpoints)) will be summarized by study arm, using mean (standard deviation (SD)) or median (inter quartile range (IQR)) for continuous variables and frequency (%) for categorical variables. Repeatedly measured variables will be summarized using descriptive statistics by study arm and by time point (baseline, 3 months, and 6 months). The mean percent

change in NT-proBNP at 6 months from baseline will be estimated in each arm along with the standard deviation. The mean percent change in NT-proBNP will be compared between 2 arms by two-sample t-test. Linear regression model will be used to compare the 2 arms in the mean percent change, adjusting for stratification factors. Those without 3-months or 6-months NT-proBNP may be imputed, using last observation carried forward method or other methods.

Compliance is defined as the total number of medications taken divided by the total number of medications provided during 6 month treatment period. The proportion of patients maintaining at least 70% compliance will be estimated in each arm. Proportion of patients experiencing each type of side effects will be estimated in each arm along with 95% confidence interval (CI). The change from baseline to 3 months and the change from baseline to 6 months in variables described in secondary objectives will be compared within each arm by paired t-test or Wilcoxon signed-rank test for continuous variables and Mantel-Haenszel test for categorical variables. Generalized linear mixed effects models will be used to compare two arms in repeatedly measured outcomes over time. P-values less than 0.05 will indicate statistical significances. SAS 9.4 (Cary, NC) and other relevant software will be used for statistical analysis.

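### The strain endpoint counts a 15% change in either direction, so its rate in each arm cannot tell improvement from deterioration

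*Combined protocol and SAP*

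**What the plan says.** Three places in the combined protocol and SAP define the strain criterion.

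- Section 2.0, secondary objective 2b: "Significant change will be defined as a change in global longitudinal strain by 15" per cent.
- Section 2.0, secondary endpoint 2: "change (significant change or non-significant change) in global longitudinal myocardial strain assessment of the left and right ventricle", at 3 and 6 months.
- Section 9.2.2: "Myocardial strain assessment- response will be defined as a change in global longitudinal strain by 15" per cent.

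None gives a direction, and none says whether 15% is relative to baseline or in strain units. By contrast, section 9.1.1 is signed: "response will be defined as a reduction in plasma 5-HIAA of 30" per cent.

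Section 11.2 adds no rule on direction. It states that "secondary endpoints (absolute changes and percent changes for continuous endpoints)) will be summarized by study arm", with frequencies for categorical variables. It also states that "Repeatedly measured variables will be summarized using descriptive statistics by study arm and by time point", plans within-arm tests of change, and plans generalized linear mixed models to compare the arms. It does not say in which form strain enters those models.

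**The concern.** A responder-type rate is useful only if the reader knows which way the counted patients moved. Here the two levels are *changed by 15%* and *did not*. A higher rate on telotristat could mean better or worse ventricular function, and equal rates could conceal opposite effects.

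The word *response* in 9.2.2 may be meant to cover favourable change only, but objective 2b and endpoint 2 speak only of significant change. The two readings count different patients. If the choice between them, or between the category and the measured value, is left until the data are unblinded, it can be influenced by the results.

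**Working it through.** **The plan's own figures.** No rate, SD, effect or power is stated for strain. The only power calculation concerns NT-proBNP (section 11.1): effect size 20/25 = 0.8, two-sided alpha 0.05, 52 evaluable patients. With 26 per arm, the noncentral t distribution gives 80.7% power, which reproduces the stated 80%. I borrow 26 per arm (52/2) below; everything else about strain is assumed.

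**Step 1: counts, with no distribution assumed.** Arm A has 8 improved and 2 worsened; arm B has 2 improved and 8 worsened. The undirected rate is (8+2)/26 = (2+8)/26 = 38.5% in both.

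**Step 2: the general result.** Let X be the percent change in strain, positive meaning better, with mean μ and SD σ. The undirected rate is P(X > 15) + P(X < −15). If X is distributed symmetrically about μ, replacing μ by −μ swaps the two terms and leaves the sum unchanged, whatever σ is.

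**Step 3: illustration.** Assume X is normal, with mean +10 or −10 on drug and 0 on placebo. At σ = 15:

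- Drug, μ = +10: improved 1 − Φ((15 − 10)/15) = 36.9%; worsened Φ((−15 − 10)/15) = 4.8%; sum 41.7%.
- Drug, μ = −10: improved 4.8%; worsened 36.9%; sum 41.7%.
- Placebo, μ = 0: 15.9% each way; sum 31.7%.

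The declared rate is therefore 41.7% against 31.7% (about 10.8 against 8.2 patients of 26), whether the drug helps or harms. Counting favourable change only, the harmful case shows 4.8% against 15.9% responding. Worsening of 36.9% against 15.9% is then hidden among the non-responders.

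**Step 4: power for a beneficial shift**, 26 per arm, two-sided 0.05. The two binary codings use exact enumeration of the pooled z-test. Three categories use the Mantel-Haenszel mean-score test with scores −1, 0, 1 (200,000 simulations). Continuous change uses the noncentral t.

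| Shift, SD | Undirected rate, drug vs placebo | Power: undirected | Favourable only | Three categories | Signed continuous |
|---|---|---|---|---|---|
| 10, 10 | 31.5% vs 13.4% | 36.8% | 66.2% | 72.0% | 94.2% |
| 10, 15 | 41.7% vs 31.7% | 12.4% | 42.9% | 52.3% | 65.4% |
| 10, 20 | 50.7% vs 45.3% | 6.1% | 28.9% | 35.2% | 42.4% |
| 5, 15 | 34.4% vs 31.7% | 6.0% | 14.2% | 17.1% | 21.8% |
| 15, 15 | 52.3% vs 31.7% | 32.5% | 78.5% | 85.8% | 94.2% |

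In the second row, the rise from 12% to 52% comes from restoring direction. The rise from 52% to 65% is the ordinary cost of using categories.

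**The case against.** The best counter-argument is that measured strain is already largely covered. Objective 2 names it: "To evaluate changes in echocardiographic parameters (CVHD score, global longitudinal myocardial strain assessment of the Left and right ventricle/TAPSE". Section 11.2 says that "variables described in secondary objectives will be compared within each arm by paired t-test or Wilcoxon signed-rank test for continuous variables". A derived change category has no baseline value, so a within-arm test of change from baseline must use the measured values. Signed strain could well be summarised and tested. That stands as a limit on the point. It does not repair the endpoint, because endpoint 2 declares strain as a category, while absolute and percent changes are promised only for continuous endpoints.

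Second, *response* can fairly be read as improvement. On that reading the rate does identify benefit, and the power gap at shift 10, SD 15 narrows to about 43% against 52%. The 12% figure belongs to the literal reading only. But the intention is not written down, and deterioration would still be merged with stability.

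Third, the CVHD (9.2.1) and 6MWT (9.3.1) criteria are also unsigned. That is true, but their declared endpoints are plain changes from baseline, so direction survives there.

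Finally, the power figures are hypothetical and the pooled z-test is not a planned test. Both are correct; steps 1 and 2 do not depend on them.

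**Conclusion.** The point holds. Followed as written, the strain rule pools deterioration with improvement and gives an arm rate that cannot be interpreted as benefit or harm. This follows from the definition alone. The equality of rates for +d and −d needs only symmetry.

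The size of the power loss is illustrative. It rests on an assumed normal distribution, assumed shifts of 5 to 15 and SDs of 10 to 20 (% of baseline), and a borrowed 26 per arm. Across the scenarios shown, undirected coding has 6% to 37% power, against 22% to 94% for signed continuous change.

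Strain is one component of one secondary endpoint. The NT-proBNP analysis and the sample size are untouched. It should be corrected, but it does not threaten the trial's main conclusion.

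**What to change.** Amend the strain text in sections 2.0, 9.2.2 and 11.2 before unblinding.

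1. Make the endpoint the signed continuous change from baseline, for the left and right ventricle separately, and state the sign convention.
2. Compare the arms with the mixed model already planned, adjusted for baseline strain and the two stratification factors (age group and disease status, section 6.2.1).
3. Take 6 months as the all-patient comparison, since both echocardiography groups are scanned at baseline and 6 months (section 8.13). The CS group has no 3-month scan. Restrict any 3-month comparison to a CHD group fixed from baseline data only: section 8.6 uses NT-proBNP above 260 without tying it to baseline, so membership could otherwise depend on a post-randomisation value of the primary outcome variable.
4. If the 15% threshold is kept, report improved, unchanged and worsened for each ventricle, and state whether 15% is relative to baseline.

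The minimum repair is item 4 with the sign convention from item 1; items 1 to 3 also recover the information lost by categorising. The cost is a short amendment and minor programming. Strain of both ventricles is already measured at baseline and follow-up (sections 7.7, 8.6 and 8.7), so no new visits, tests or patients are needed.
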